6.1.2 Derivation of outcome measures

The key outcome measure will utilise three measures from the cycle ergometer. MVIP prior to exercise at the baseline test baseline ($MVIP_{FRESH}$), the standard cycle ergometer measure of power at $\dot{V}O_{2\text{peak}}$ ($P-\dot{V}O_{2\text{peak}}$) and MVIP in the fatigued state, instantaneously at the point of $\dot{V}O_{2\text{peak}}$ at task failure ($MVIP_{FATIGUE}$) will be recorded as described in Figure 1.

The presence of a power reserve or not will be determined by a difference of >40% difference between $P-\dot{V}O_{2\text{peak}}$ and $MVIP_{FATIGUE}$.

6.1.3 Primary outcome analyses

This will describe the clinical and exercise phenotype of participants in whom fatigue (no power reserve; muscle-limited) or dyspnoea (large power reserve; symptom-limited) predominate as the operant mechanism, and how the groups (patients v controls and participants with dyspnoea or fatigue as limiting symptoms) differ.

6.1.4 Secondary outcome analyses

This will explore relationships between the power variables (e.g. MVIP_{FRESH}, P- $\dot{V}\text{O}_{2\text{peak}}$, MVIP_{FATIGUE}), ventilatory and pulmonary gas exchange variables (e.g. $\dot{V}\text{O}_2$, $\dot{V}\text{CO}_2$, $\dot{V}\text{E}$, RER, tidal volume, breathing frequency), and clinical variables in the CHF participants and controls.

6.2 Objective 2

6.2.1 Endpoints for objective 2

Exercise time sustained at the required power during the maximum effort constant power tests.

6.2.2 Derivation of outcome measures

This will be measured from when the required power is applied to the cycle ergometer power until the point of intolerance, when the required power will be removed.

6.2.3 Primary outcome analysis

This will be the change in exercise tolerance time between the two constant power tests (dihydrocodeine vs. placebo).

6.2.4 Secondary outcome analyses

The secondary outcomes will include a comparison of the power variables (e.g. MVIP_{FRESH}, P- $\dot{V}\text{O}_{2\text{peak}}$, MVIP_{FATIGUE}), ventilatory and pulmonary gas exchange variables (e.g. $\dot{V}\text{O}_2$, $\dot{V}\text{CO}_2$, $\dot{V}\text{E}$, RER, tidal volume, breathing frequency) and perceived symptom scores at baseline and intolerance between the tests following

dihydrocodeine and placebo. We will also include comparison of the power variables (e.g. MVIP_{FRESH}, P- $\dot{V}O_{2\text{peak}}$, MVIP_{FATIGUE}), ventilatory and pulmonary gas exchange variables (e.g. $\dot{V}O_2$, $\dot{V}CO_2$, $\dot{V}E$, RER, tidal volume, breathing frequency) and perceived symptom scores at baseline and isotime to investigate whether the rate at which variables are achieved is different between dihydrocodeine and placebo.

6.3 Missing data

The percent of missing data for each variable will be recorded. If there is a large number of missing data on variables, an evaluation on the missing data will be conducted before analysis. Patients who did not attend all tests will be reported along with their reasons for not attending.

7 Populations

7.1 Intention-to-treat population

The primary method for analysing the trial data (objective 2) will be the Intention-to-treat analysis (ITT). All subjects who completed the first two constant power tests will be included in the intention-to-treat population (ITT) according to intention-to-treat principles, in which subjects will be analysed according to the test assigned by randomization (dihydrocodeine or placebo). Participants who withdraw consent for their data to be used in the trial will not be included in the ITT population.

7.2 As-treated population

The as treated population is all patients being reported with the treatment in which they received.

8 Data handling

8.1 Data validation

Baseline and follow up data will be captured using an excel spreadsheet. The data will be exported to specific statistical software for analysis (e.g. STATA, SPSS, Origin, and MATLAB). Data cleaning will involve checking for incompleteness, inconsistencies and inaccuracies. Inaccuracies and inconsistencies will be reported back to the primary investigators. Validation checks will include:

- Checking eligibility of all randomised patients
- Checking on 1:1 cross-over randomisation to see if it was achieved
- Checking for outliers
- Checking on missing data

8.2 Data analysis

8.2.1 General calculations

Categorical data will be summarised in terms of the number of patients and percentages. All percentages will be calculated using as the denominator the total number of patients within the specified analysis population; that is including patients with missing data. Baseline grouping will be patients with CHF and control subjects.

Normality for all continuous variables will be tested using the Shapiro-Wilk test, histograms, Q–Q plots and boxplots. Normally distributed continuous variables will be reported as mean and $\text{mean} \pm 1 \text{ SD}$, and if there are non-normally distributed continuous variables these will be reported as median (interquartile range). Subsequently, associations between groups or interventions and baseline characteristics will be assessed using either analysis of variance and the 2-sample Student t test for normally distributed values. In cases of non-normally distributed data

log-transformations or equivalent non-parametric test will be considered. Similar associations with categorical variables will be analysed using the chi-squared test for contingency tables.

All statistical tests performed will be two-sided tests at a 5% significance level and giving the 2-sided 95% confidence intervals. These tests and confidence intervals will be displayed to 2 decimal places, along with standard errors, standard deviations and parameter estimates. Any presented p-value will be given to 3 decimal places, any p-value lower than 0.001 will be shown as <0.001. Analysis will be conducted using specific statistical software for analysis (e.g. STATA, SPSS, Origin, and MATLAB)

8.2.2 Baseline characteristics

Demographic baseline characteristics will be presented in a table.

8.2.3 Recruitment and compliance

The flow of patients throughout the study from randomisation to analysis will be displayed in a CONSORT diagram.

Summaries of the compliance of the patients and the treatment in which they all received will be shown in tables for each randomised arm. If any reasons why patients were not compliant or why they received a different treatment are collected then they will also be summarised.

8.2.4 Objective 1 analyses

These will use the power reserve to describe the frequency of fatigue vs. dyspnoea limitations to $\dot{V}O_{2\text{peak}}$ in CHF compared with controls and also compare the magnitude of the power reserve along with relevant clinical characteristics of participants with either limiting factor using appropriate tests depending upon the nature of the data.

We will then proceed to explore the relationships between the relevant clinical characteristics, the power reserve, other power variables (e.g. MVIP_{FRESH}, P- $\dot{V}O_{2\text{peak}}$, MVIP_{FATIGUE}) and ventilatory and pulmonary gas exchange variables (e.g. $\dot{V}O_2$, $\dot{V}CO_2$, $\dot{V}E$, RER, tidal volume, breathing frequency).

All model assumptions will be checked to ensure the residuals are normal, and that the residuals are independent with no evidence of homoscedasticity.

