In CHF opioids reduced symptoms of dyspnoea,[17] increase exercise time (~12 % increase in tolerable duration) and $\dot{V}O_{2\text{peak}}$ [18] ($+1.6 \text{ ml} \cdot \text{min}^{-1} \cdot \text{kg}^{-1}$; MCID = $1 \text{ ml} \cdot \text{min}^{-1} \cdot \text{kg}^{-1}$ [19]). However, similar to the variable response seen in COPD, the effect is inconsistent across CHF patients, possibly due to the heterogeneity in the mechanism of exercise limitation that has previously not been discernible. We believe that we can now divide CHF patients into two groups using our novel CPX approach (Figure 2).

Compared with alternative interventions (e.g. device, medical, rehabilitation) that affect *both* fatigue and dyspnoea in combination, opioid treatment specifically targets dyspnoea. Thus, objective 2 aims to demonstrate that our CPX-test can for the first time identify likely 'responders' (symptom-limited) and 'non-responders' (muscle-limited) to this mechanism-specific, symptom-alleviating opioid intervention (*Objective 2*) whilst also confirming our hypothesis of two phenotypes within the exercise intolerance CHF population. This will also provide the first evidence that the mechanisms limiting exercise tolerance in CHF are directly modifiable and can be selectively targeted by personalised interventions to maximise therapeutic efficacy.

3 Study design and randomisation

Design: This study is a randomised, double-blinded, crossover, multi-group trial conducted at one centre in the UK (Leeds Teaching Hospitals NHS Trust).

Participants: The study will recruit a total of 100 subjects of whom 75 will have HF with reduced ejection fraction (HFrEF) and 25 will be control subjects.

Inclusion criteria: Patients with CHF due to left ventricular systolic dysfunction (NYHA II or III, and left ventricular ejection fraction < 50%), optimally tolerated stable medical therapy, able and willing to provide written informed consent and perform CPX-tests.

Exclusion criteria: CHF without symptoms or class IV symptoms, any contraindications to exercise or severe neuromuscular disability limiting exercise, significant COPD (FEV1 < 50%) or other significant respiratory disease contributing to symptoms, or renal disease (eGFR < 20).

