5.1 Objective 1: Phenotyping the mechanism of exercise limitation

To identify if the power reserve is different between CHF patients vs. controls (two-tailed independent t-test), assuming a standard deviation of 40% (based on our CHF pilot data) we require 60 CHF and 20 control patients to have 90% power to detect an absolute power reserve difference of 30% at $p < 0.05$. The 3:1 ratio allows adequate power for our secondary analysis comparing the 3 different severities of CHF, where 20 in each group gives us 80% power to detect a linear trend over the 3 categories of increasing severity, with a mean power reserve difference of 20 percentage points in absolute terms between each group, e.g. 20 % vs 40 % vs 60 % power reserve with increasing severity. In anticipation that we may need to log-transform our primary outcomes due to non-normally distributed data, our power calculation is conservative. To allow for any drop-out, and any unsuccessful test, we propose recruiting an additional 25% (*Objective 1*). Hence, we will invite 75 people with CHF and 25 controls to participate.

5.2: Objective 2: Efficacy of intervention

Based on exercise on a conservative effect size (f) of 0.300,[18] and a conservative correlation between repeated measures of 0.5,[14] 17 patients in each group gives us 90% power at $p < 0.05$. Thus, we will be powered to detect a smaller increase in

exercise duration than that found in COPD.[14] We will recruit 20 patients to allow for any drop-out (*Objective 2*).

6. Planned analyses

6.1 Objective 1

6.1.1 Endpoints for objective 1

In *Objective 1* we will use the power reserve to describe the frequency of muscle-limited vs. dyspnoea (symptom)-limited CHF patients and controls and describe these phenotypes by clinical severity and cardiopulmonary variables.

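### Section 8.2.4 compares the size of the power reserve between groups defined by that reserve, so the p-value is uninformative; the CHF-versus-control comparison that sized Objective 1 is not explicitly carried into 6.1.3 or 8.2.4

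*SAP*

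**What the plan says.** **How the groups are formed.** SAP 6.1.2: "The presence of a power reserve or not will be determined by a difference of >40% difference between" the ramp power at peak and the fatigued isokinetic power (MVIP_FATIGUE). Section 6.1.3 equates fatigue or muscle limitation with no reserve, and dyspnoea or symptom limitation with a large one. No other variable enters the classification.

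**What is compared.** Section 6.1.3 says the primary Objective 1 analysis will describe "how the groups (patients v controls and participants with dyspnoea or fatigue as limiting symptoms) differ". It names neither an outcome variable nor a test for either contrast. Section 8.2.4 first describes how often each limitation occurs in CHF compared with controls, and then says the analyses will "compare the magnitude of the power reserve along with relevant clinical characteristics of participants with either limiting factor using appropriate tests".

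**What Objective 1 was sized on.** Section 5.1 gives the purpose of the calculation as "To identify if the power reserve is different between CHF patients vs. controls (two-tailed independent t-test". Its inputs are a pilot-based SD of 40 percentage points, a difference of 30 points and a 5% level. From these it concludes: "we require 60 CHF and 20 control patients to have 90% power". This is a comparison of means of the continuous reserve. Section 6.1.1 frames the endpoint as the frequency of the two limitations in patients and controls.

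**The concern.** There are two linked faults.

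1. **Circularity.** If participants are split at a reserve of 40% and the reserve is then tested between the two halves, every value in one half exceeds every value in the other by construction. A significant result follows from the cut. It would appear equally in a population with a single smooth distribution of reserve and no phenotypes.

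2. **The sized comparison is not carried through.** The test that justified 60 patients and 20 controls appears in 5.1 only. Where the analyses are set out, CHF versus controls appears as a frequency (6.1.1, 8.2.4) or without a variable (6.1.3). An analyst working from 8.2.4 could reasonably report a dichotomised comparison and never run the one the trial was sized for.

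At stake are a p-value that looks like evidence and is not, and a main Objective 1 comparison that the plan leaves open.

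**Working it through.** **Inputs.** From 5.1: difference 30 percentage points, SD 40, 60 CHF and 20 controls, two-sided 5%. From 6.1.2: cut at 40%. From the pilot data in the Rationale: reserve mean 101%, SD 122%, expressed as a percentage of ramp power at peak. Assumed, because the SAP does not give them: the shape of the distribution, and the control mean (varied over 0-30%).

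**Step 1: the plan's own power figure.** Noncentrality = 30 / (40 × √(1/60 + 1/20)) = 30 / (40 × 0.2582) = 2.905. Normal approximation: Φ(2.905 − 1.960) = 0.828. Noncentral t on 78 df: 0.818. The stated 90% is not reproduced; the two-sided t-test has about 82%. That is a separate defect of 5.1 and adds no weight here, but 82% is the right benchmark for step 4.

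**Step 2: the built-in difference.** Take one normal population with mean μ and SD 40, and cut it at 40. With z = (40 − μ)/40, the expected gap between the two halves is 40 × [φ(z)/(1 − Φ(z)) + φ(z)/Φ(z)]. At μ = 40, z = 0 and the gap is 40 × (0.798 + 0.798) = 63.8 points. For μ of 0, 20, 60 and 100 it is 72.5, 66.0, 66.0 and 83.1. The cut alone creates a gap at least twice the 30 points the trial was sized to detect.

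**Step 3: rejection rates with no phenotypes present.**

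| Single homogeneous population | n | t-test | Rank test |
|---|---|---|---|
| Normal, SD 40, mean 0 to 100, p < 0.05 | 60 or 80 | 100% | 100% |
| Log-normal power ratio, reserve mean 101, SD 122, p < 0.001 | 60 | 99.7% | 100% |
| Log-normal reserve, mean 101, SD 122, p < 0.05 | 60 | 98.9% | 100% |
| Log-normal reserve, mean 101, SD 122, p < 0.05 | 16-20 | 63-75% | 100% |

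The normal and log-normal-reserve rows count runs with at least two participants in each half. With CHF and controls both drawn from a normal distribution with mean 40 and SD 40 (60 and 20), the CHF-versus-control t-test rejected in 5.2% of runs, as it should. The test between the halves rejected in 100% of the same runs.

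**Step 4: what testing only the frequency would cost.** With normal reserves, SD 40 and CHF 30 points above controls, the proportion above 40% is 1 − Φ((40 − mean)/40).

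| Assumed control mean | Controls > 40% | CHF > 40% | Chi-squared power, 60 vs 20 |
|---|---|---|---|
| 0 | 15.9% | 40.1% | 53% |
| 10 | 22.7% | 50.0% | 58-59% |
| 20 | 30.9% | 59.9% | 62% |
| 30 | 40.1% | 69.1% | 65% |

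Against 82% for the t-test, the loss is 82 − 65 = 17 to 82 − 53 = 29 percentage points.

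**Step 5: how firm that loss is.** With a log-normal power ratio, CHF mean 101, controls 30 points lower and the pilot SD of 122 in both groups, the raw t-test has about 16-17% power and chi-squared about 22%, so the order reverses. With controls of mean 30 and SD 40 instead, the t-test has about 87% and chi-squared 66%.

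**The case against.** **The sentence can be read another way.** In 8.2.4 the comparison of magnitude follows directly on the phrase about CHF and controls. It could continue that contrast, with the limiting-factor phrase attached only to the clinical characteristics. The sized comparison would then be present and nothing would be circular. This reading is possible but less natural. If both can be held, the section has not fixed its comparison, and the same rewording cures it.

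**The sized comparison is named.** A reader might infer that it is missing from the plan altogether. That goes too far: 5.1 names it with its test, 6.1.3 lists patients against controls, and 8.2.1 offers a two-sample t-test with log-transformed or non-parametric alternatives, though in terms of baseline characteristics. What stands is that no analysis section joins the variable, the contrast and the test.

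**Nothing makes a chi-squared test primary.** A reader might infer that the t-test has been replaced by a dichotomised one. The document does not say so. It says frequencies will be described, so the 53-65% applies only if that were the sole comparison tested.

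**Objective 1 is largely descriptive.** This is true of 6.1.1 and 6.1.3, but 8.2.4 asks for tests and 8.2.1 makes all tests two-sided at 5%. It is also tempting to link the circular p-value to the Rationale's phrase "whilst also confirming our hypothesis of two phenotypes within the exercise intolerance CHF population". That sentence concerns Objective 2 and the response to the opioid. The SAP does not say the 8.2.4 comparison will serve as that confirmation.

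**The test does not reject with literal certainty.** This is correct for an equal-variance t-test on small, skewed samples. At the planned size rejection is close to certain, and the p-value is uninformative at any size.

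**Conclusion.** The point holds in two parts of different strength.

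The circularity is firm on the natural reading of 8.2.4. At n = 60, a population with no phenotypes gives rejection at 5% in about 99-100% of samples with the ordinary t-test and 100% with a rank test. This does not rest on a particular distribution, because the cut separates the groups whatever the shape.

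The failure to carry over the 5.1 comparison is a gap between sections: the comparison exists but is not explicitly placed among the analyses. Its possible cost, 82% power falling to 53-65%, assumes normality, the plan's SD of 40 in both groups, a 30-point difference and control means of 0-30%. With the pilot SD in both groups the ordering can reverse, so these figures illustrate the risk and are not a fixed loss. The case for naming the comparison is that the trial was sized on it.

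The documents do not support saying that the trial has abandoned its sized test, or that it plans to claim two phenotypes from this p-value. This is a correction that should be made before analysis; it does not undermine the design.

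**What to change.** In 6.1.3 and 8.2.4:

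- Name the CHF-versus-control difference in continuous power reserve as the primary Objective 1 comparison, using the 5.1 independent t-test or its log-scale version, which 5.1 and 8.2.1 already anticipate. State how the scale will be chosen.
- Report the frequency of reserve above 40% in each group, with confidence intervals, as descriptive.
- Show the reserve by limiting-factor group as a summary or plot of the whole distribution, without a p-value.
- Between those groups, test only variables that do not enter the definition. This excludes the reserve. MVIP_FATIGUE and ramp power at peak may be shown, but should not be offered as evidence of distinct phenotypes because the reserve is computed from them.

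The cost is SAP wording only. No data collection or sample size changes, and the one p-value lost carried no information.

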Thus, exercise limitation in CHF is a complex interplay between increased fatigue and increased dyspnoea. Which operant mechanism predominates is currently unknown, cannot be identified by traditional CPX-tests, and might be different between patients in whom the severity of exercise limitation is the same. Using our innovative CPX approach can now make the distinction between intolerable fatigue (i.e. muscle limited) or dyspnoea (i.e. symptom limited by breathlessness).

CHF pilot data: In contrast to the response seen in health, in CHF patients (n=16), we have shown that ramp-incremental exercise is terminated at $\dot{V}O_{2\text{peak}}$ with a large power reserve. MVIP_{FATIGUE} was, on average, $101\pm122\%$ greater than P- $\dot{V}O_{2\text{peak}}$ (213 ± 132 vs. 109 ± 44 Watts, RM-ANOVA with Dunnett *post-hoc*,[7] $p = 0.002$, 95% CI_{Difference} 38, 171 Watts; Figure 2). This power reserve suggests the physiologic and sensory responses have become dissociated and $\dot{V}O_{2\text{peak}}$ is symptom-limited in CHF. This is similar to our observation in COPD patients where MVIP_{FATIGUE} was $\sim 160\%$ greater than P- $\dot{V}O_{2\text{peak}}$ at task failure.[8]

[figure not shown]

Figure 2: Representative examples of CHF patient responses to our innovative ramp-incremental CPX test. Fresh maximal voluntary isokinetic power (□ MVIP_{FRESH}) decreases as the test progresses. **A.** Fatigued maximal voluntary isokinetic power (□ MVIP_{FATIGUE}) at $\dot{V}O_{2\text{peak}}$ (○) is greater than the ramp-incremental power (P- $\dot{V}O_{2\text{peak}}$): the power reserve suggests exercise in this patient is symptom-limited. **B.** MVIP_{FATIGUE} was not meaningfully different from P- $\dot{V}O_{2\text{peak}}$: the absence of a power reserve suggests exercise in this patient is muscle-limited.

In our CHF patients, we also observed two key phenotypes:

1. CHF patients ($n = 6$) without a power reserve ($MVIP_{FATIGUE} 22 \pm 12\%$ greater than $P\dot{V}O_{2\text{peak}}$ at task failure; 141 ± 66 vs. 115 ± 47 Watts $p = 0.547$, $CI_{\text{Difference}} -44, 97$ Watts), suggesting they reached their physiological limits and are muscle-limited (Figure 2B).

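### SAP 8.2.4 plans to relate the power reserve to P-VO2peak and MVIP_FATIGUE, the two quantities it is calculated from, so a zero-correlation test of either pair is uninformative.

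*SAP*

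**What the plan says.** SAP 6.1.2 defines the classification from two measurements: "The presence of a power reserve or not will be determined by a difference of >40% difference between" P-VO2peak and MVIP_FATIGUE. The pilot data in section 2 give the scale: "MVIP_{FATIGUE} was, on average, $101\pm122\%$ greater than P"-VO2peak. P-VO2peak is therefore the denominator.

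SAP 8.2.4 then plans to "explore the relationships between the relevant clinical characteristics, the power reserve, other power variables", with MVIP_FRESH, P-VO2peak and MVIP_FATIGUE as the listed examples, together with ventilatory and gas exchange variables. Section 8.2.1 puts every test at a two-sided 5% level, and section 8.3 makes no multiplicity adjustment. Nothing in the SAP takes the reserve-versus-component pairs out of testing or gives a reference value other than zero for them.

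Section 6.1.4 ("This will explore relationships between the power variables") covers the same families of variables but does not name the reserve. Section 5.1 mentions a secondary analysis "comparing the 3 different severities of CHF", with the reserve as outcome, and does not define the three categories.

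**The concern.** Write M for MVIP_FATIGUE and P for P-VO2peak. The reserve is R = 100 × (M/P - 1). If M and P vary independently, R still falls as P rises and rises as M rises, because each is a term in R. A p-value against zero for R with M, or R with P, therefore does not show whether the reserve carries information beyond its components. It reflects their relative spread and how they move together, which a direct analysis of M against P shows without the detour.

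The reserve is the trial's central construct: it classifies patients as muscle-limited or symptom-limited. A published correlation between reserve and peak power could be read as a finding about mechanism when much or all of it is built into the calculation.

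**Working it through.** **Inputs (SAP section 2, CHF pilot, n = 16).** M and P: "213 ± 132 vs. 109 ± 44 Watts". Paired difference: "95% CI_{Difference} 38, 171 Watts". The analysable CHF sample is 60 (section 5.1).

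**Step 1: confirm the scale of the reserve.** The pilot subgroups are 22 ± 12% (n = 6) and 149 ± 134% (n = 10).
- Pooled mean: (6 × 22 + 10 × 149)/16 = 101.4%.
- Pooled SD: √{[5 × 12² + 9 × 134² + 6 × (22 - 101.4)² + 10 × (149 - 101.4)²]/15} = 121.9%.

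Both match the reported 101 ± 122%, so the reserve is a percentage of P computed patient by patient.

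**Step 2: how far the components correlate in the pilot.** The half-width of the interval is (171 - 38)/2 = 66.5 W. The SD of the difference is 66.5 × √16 / c, where c is the critical value, and r = (132² + 44² - SD²)/(2 × 132 × 44).
- Paired t on 15 df, c = 2.131: SD = 124.8 W, r = 0.33.
- Dunnett, c = 2.32 (assumed; the SAP does not give it): SD = 114.7 W, r = 0.53.

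**Step 3: the built-in correlation on the log scale.** For log-normals with these moments, the variance of log M is ln(1 + (132/213)²) = 0.325 and that of log P is ln(1 + (44/109)²) = 0.151. With independent components:
- corr(log M/P, log P) = -√(0.151/0.476) = -0.56
- corr(log M/P, log M) = +√(0.325/0.476) = +0.83

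**Step 4: simulation on the percentage scale.** Log-normal M and P with the pilot moments, n = 60, R as defined, Pearson correlation tested against zero at 5%:

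| Component correlation r | R with M (significant) | R with P (significant) |
|---|---|---|
| 0 | +0.80 (100%) | -0.46 (99%) |
| 0.33 | +0.73 to +0.74 (100%) | -0.28 to -0.29 (62–64%) |
| 0.53 | +0.71 (100%) | -0.13 (14–15%) |

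Ranges are differences between repeated simulations. At r = 0 the direct test of M against P rejects in the nominal 5%. At r = 0.6 the correlation of R with P is about -0.07, and at r = 0.8 it is +0.23. The result for R with P is thus a restatement of r and the two spreads, and it can vanish or change sign.

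**Step 5: severity, on assumptions the SAP does not make.** Suppose the three categories are thirds of a measure that correlates 0.5 to 0.9 with log P and is related to M only through P. A trend test on R then rejects in about 41–93% of runs at r = 0, 17–48% at r = 0.33 and 7–13% at r = 0.53. If severity is unrelated to P, it rejects in about 5%.

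**The case against.** The case for leaving the plan alone has four parts.

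*The SAP only explores.* Section 8.2.4 names four families of variables and no specific correlation, model or null. That is so, and the analysis is secondary. But both components are named beside the reserve, and section 8.2.1 puts all tests at 5%, so the natural execution includes these pairs.

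*Independence is not what the pilot shows.* This stands. At r = 0 the simulated reserve is 127% (SD 177%), against the pilot's 101% (SD 122%). At r = 0.33 it is 110% (SD about 129%), much closer. A reader might infer that a strong correlation with P-VO2peak is assured; at the pilot-implied values it is weak to modest. The correlation with MVIP_FATIGUE stays strong throughout.

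*The severity trend is not shown to be spurious.* A reader might infer that a severity gradient must appear, and that the rejection rates in step 5 are false-positive rates. The documents support neither. The categories are undefined, and both the grading by exercise capacity and its correlation with peak power are assumptions. Section 1 ties severity to exercise intolerance, and only two NYHA classes are eligible, so such grading is plausible but not stated. Moreover, in step 5 the reserve as defined truly differs between categories: at r = 0 and severity correlation 0.5 the means are 176/124/83% from low to high capacity. A patient who stops at lower power with undiminished MVIP_FATIGUE does have more reserve by the SAP's definition.

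*Adjustment changes the question.* Regressing log MVIP_FATIGUE on log P-VO2peak plus a covariate conditions on part of the reserve. That is a reason not to make it the main analysis for every clinical relation.

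**Conclusion.** The point holds for two pairs: reserve with MVIP_FATIGUE and reserve with P-VO2peak. A test of zero correlation for either is uninformative because of how the reserve is calculated. The first pair will be significant almost whatever the data (+0.7 to +0.8, 100% of runs at all three component correlations tabulated). The second ranges from -0.46 (99% significant) under independence to -0.13 (14%) at a component correlation of 0.53. These sizes rest on log-normal components with the moments of a 16-patient pilot, n = 60, and for the 0.53 value an assumed Dunnett critical value.

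It does not extend to everything in 8.2.4. MVIP_FRESH, gas exchange and clinical variables are not terms in the reserve, and those unrelated to both components are unaffected. Section 6.1.4 does not name the reserve and is not at fault. On severity there is only a conditional caution: if the categories are graded by exercise capacity, a gradient in reserve could come from lower peak power alone, and the report should let the reader see that.

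**What to change.** In SAP 8.2.4, state that the power reserve will not be tested against P-VO2peak or MVIP_FATIGUE, and that the relation between these two will be analysed directly, for example by regressing log MVIP_FATIGUE on log P-VO2peak.

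Define the three severity categories of section 5.1. If they are graded by exercise capacity, report MVIP_FATIGUE and P-VO2peak separately by category beside the reserve. Add log MVIP_FATIGUE adjusted for log P-VO2peak as a sensitivity analysis; in the step 5 scenarios this model rejected in 4–6% of runs, close to nominal.

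The cost is SAP wording and slightly more reporting, with no new data. The adjusted model asks whether MVIP_FATIGUE differs at a given peak power, which is a different question from the percentage reserve, and the report should say so.
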